IMAGING TAU IN ALZHEIMER'S DISEASE AND NORMAL AGING

NCT03373604

Date: December 21, 2022

Background

While amyloid plaques are a pathological hallmark of Alzheimer's disease (AD), whether β -amyloid is the causal agent of neurodegeneration in AD remains unclear. Evidence supporting the hypothesis that amyloid is a primary contributor to AD pathogenesis (the amyloid-first hypothesis) include the finding that genetic mutations responsible for inherited forms of AD cause increased amyloid production. Studies using positron emission tomography (PET) to measure amyloid plaque burden in vivo have demonstrated amyloid positivity before obvious atrophy or cognitive decline in healthy older controls. While tau positive neurofibrillary tangles represent the second hallmark of AD, tau mutations are seen in patients with variants of frontotemporal dementia, not AD. The propagation of tau pathology is thought to follow amyloidosis, suggesting amyloid in some way induces tau mediated degeneration. However, the link between amyloid and tau not clear as there are spatial and temporal distinctions. For example, bulk of amyloid burden in medial parietal cortex and frontal cortex early on, while tau burden begins in medial temporal cortex.

While β -amyloid has been shown to have direct neurotoxic effects in vitro, these effects are seen at concentrations of β -amyloid much higher than found in human brain[1]. Therefore, amyloid may not confer significant direct toxicity. In addition, autopsy findings of pre-tangle pathology occurring in midlife prior to amyloidosis[2] suggest that tauopathy may begin prior and independent to significant amyloid plaque deposition. Since amyloid burden correlates poorly with cognition[3], tau may be a more important mediator of neurodegeneration in AD.

Investigational Agent

^{18}F -MK-6240 is a PET radioligand that binds to paired helical filament tau aggregates. This radioligand has only been used for research purposes. ^{18}F -MK-6240 will be administered in tracer doses ($\leq 20 \mu\text{g}$) at activity of 4 to 5 mCi (148 - 185 MBq) $\pm 10\%$ per injection.

Study Objectives

The primary objective is to determine the extent and spatial distribution of tau at different stages along the cognitive spectrum of aging (cognitively normal older adults, adults with mild cognitive impairment, and adults with Alzheimer's disease dementia).

Secondary objectives are to determine how ^{18}F -MK-6240 binding in brain relates to cognitive performance, amyloid binding, atrophy on MRI, and CSF concentrations of markers of inflammation and neurodegeneration.

Study Design

150 subjects will undergo screening including history, physical examination, routine laboratory studies, neuropsychological testing, and brain MRI.

Target sample size is 100 elders with impairment (50 amnestic MCI and 50 Alzheimer's disease) and 50 elders without impairment (150 subjects total).

One brain MRI will be performed on each subject using a 3 T Philips scanner. Sequences performed will include 3D T1 (MPRAGE, 180 slice 1 mm resolution, 256 x 256 voxel count) for volumetric analysis and clinical sequences to exclude subjects with significant intracranial pathology unrelated to AD, such as malignant brain tumor or subdural hematoma. PET scans will take place on a Biograph mCT PET scanner (Siemens Healthcare) at the CUMC Kreitchman PET Center. Subjects will have one PET scan with ^{18}F -MK-6240 (injected activity 4 to 5 mCi = 148 - 185 MBq $\pm 10\%$). PET imaging will be performed without arterial sampling. Vital signs

(blood pressure, heart rate, respiratory rate, and temperature) will be checked prior to injection of ¹⁸F-MK-6240, then at the completion of the PET scan. ¹⁸F-MK-6240 will be purchased from Cerveau Technologies, Inc. via a licensed production facility. Subjects will not be informed of ¹⁸F-MK-6240 PET scan results, as this scan is used only in research and have not yet been validated for clinical use. Subjects will be informed if a clinically important abnormality is detected on MRI or PET imaging (e.g., brain tumor).

FreeSurfer (<http://surfer.nmr.mgh.harvard.edu/>), the MRI software package comprising a suite of automated tools for segmentation, reconstruction, and derivation of regional volumes and surface-based rendering, will be used for derivation of regions-of-interest (ROIs). Eleven ROIs will be extracted from the structural T1 image: entorhinal cortex, hippocampus, inferior temporal cortex, combined superior and middle temporal cortex, superior parietal lobule, inferior parietal lobule, precuneus, occipital cortex, prefrontal cortex, striatum, and thalamus.

¹⁸F-MK-6240 PET images will be analyzed as follows: Freesurfer based ROIs will be applied to coregistered PET images. Correction for partial volume effects using a region-based voxel-wise method[23] will be applied. Regional time-activity curves using 60-120 min of scan data will be extracted from the PET scans, including cerebellum which will be used as a reference region. Standard uptake value ratio (SUVR) values will be calculated by dividing SUV values for each target region by that of the cerebellum.

Subjects will have the option of having one lumbar puncture (LP) for CSF collection. Subjects may refuse the LP and still participate in the other study procedures. CSF analysis will be performed to determine CSF concentrations of total tau, phospho-tau, β -amyloid, and markers of inflammation such as IL-1 β , TNF- α , glial fibrillary acidic protein, S100B, and YLK-40.

Primary Study Endpoints

Because the drugs used in this study are radioligands given at tracer doses, there are no clinical endpoints of the study.

The primary outcome measures are:

1. Amount of ¹⁸F-MK-6240 binding.

Secondary outcome measures are:

1. Correlation Between Tau, Neurodegeneration and Inflammation

Statistical Plan

Sample Size Determination

Because ¹⁸F-THK-5351 is a recently developed radioligand, we do not have adequate preliminary data for a formal power calculation. This protocol is designed to generate information about ¹⁸F-MK-6240 binding in a large number of subjects over the spectrum from normal aging to mild cognitive impairment to Alzheimer's disease.

Statistical Methods

The primary outcome measure will be regional standardized uptake value ratio (SUVR) values for ¹⁸F-MK-6240 using cerebellum as reference region. Multiple brain regions will be

measured, with particular attention to medial temporal cortex structures such as hippocampus and entorhinal cortex. Analysis will be performed using a one-way ANOVA with cognitive status (AD vs. MCI vs. normal) as independent variable. Effect of age and education will be determined in post-hoc analysis.

Regression models will be fit for ¹⁸F-MK-6240 binding as dependent variable and cognitive scores, voxel count on MRI, and CSF concentrations of markers of inflammation and neurodegeneration as independent variables.

References

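### Does giving 150 as both the screening number and the target, with a rationale that names another tracer, undermine the sample size?

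*Combined protocol and SAP*

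**What the plan says.** Three statements in the combined protocol and SAP bear on this.

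- **Number screened.** Study Design opens with "150 subjects will undergo screening including history, physical examination, routine laboratory studies, neuropsychological testing, and brain MRI".
- **Target.** The next sentence reads "Target sample size is 100 elders with impairment (50 amnestic MCI and 50 Alzheimer's disease) and 50 elders without impairment (150 subjects total". Later in the same section the MRI is said to include "clinical sequences to exclude subjects with significant intracranial pathology unrelated to AD, such as malignant brain tumor or subdural hematoma". No expected exclusion rate, replacement rule or upper limit on screening is given.
- **Rationale.** Under Sample Size Determination the absence of a power calculation is explained by the statement that "THK-5351 is a recently developed radioligand, we do not have adequate preliminary data for a formal power calculation". The sentence after it names 18F-MK-6240 and gives the aim as information on "binding in a large number of subjects over the spectrum from normal aging to mild cognitive impairment to Alzheimer's disease".

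The primary analysis, under Statistical Methods, is: "Analysis will be performed using a one-way ANOVA with cognitive status (AD vs. MCI vs. normal) as independent variable". No significance level, power, effect size or standard deviation appears anywhere.

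**The concern.** Read literally, 150 people enter a screening process that can remove some of them, and 150 come out. That implies a screen-failure rate of zero. If cognitive status is settled at screening, those 150 must also divide exactly into three groups of 50. A fixed intake with any unreplaced exclusion would fall short of the target.

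The rationale adds to the doubt. The only reason offered for having no power calculation concerns a tracer the study does not use, so the reader is not told whether the same holds for 18F-MK-6240.

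If both points were real defects, the group size would be overstated. Since the plan has no formal power calculation, that count is its only quantitative indication of precision. A null comparison of normal subjects with MCI could then be given more weight than the data support.

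**Working it through.** **1. The plan's own figure.** 50 + 50 + 50 = 150. The target adds up, and it equals the screening number, so the implied allowance for exclusions is 0%. Nothing else can be reproduced, because the plan gives no inputs to a power calculation.

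**2. What a literal reading would cost.** The documents give no exclusion rate, so the rate e is an assumption, varied over a range. Subjects left = 150 × (1 − e). Number to screen to end with 150 = 150 / (1 − e), rounded up.

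| Assumed e | Left of 150 | Per group | Screened to reach 150 |
|---|---|---|---|
| 2% | 147 | 49.0 | 154 |
| 5% | 142.5 | 47.5 | 158 |
| 10% | 135 | 45.0 | 167 |
| 20% | 120 | 40.0 | 188 |
| 30% | 105 | 35.0 | 215 |

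The chance that all 150 pass is (1 − e)^150: 0.99^150 = 0.221, 0.98^150 = 0.048 and 0.95^150 = 0.0005. So with a fixed intake and no replacement, some shortfall is likely even at low rates. What matters is its size.

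**3. Effect on the planned test.** Three-group ANOVA F test, with a two-sided 5% level and 80% power assumed. At 150 subjects the detectable effect is Cohen's f = 0.256. Holding f at that value and reducing the total:

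| Total | Power at f = 0.256 | f detectable with 80% power |
|---|---|---|
| 150 | 80.0% | 0.256 |
| 142.5 | 77.8% | 0.263 |
| 135 | 75.3% | 0.270 |
| 120 | 69.8% | 0.287 |
| 105 | 63.4% | 0.307 |

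For a pairwise comparison by two-sample t test under the same assumptions, the detectable difference is 0.57 SD at 50 per group, 0.60 at 45, 0.63 at 40 and 0.68 at 35. The upper rows cover the losses one might expect from the single exclusion described. Nothing in the documents supports 20% or 30%.

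**4. What depends on the 150.** A shortfall requires two things: at least one exclusion, and no replacement. The first is likely; the second is nowhere stated. The plan does not describe 150 as the number analysed. It calls it a target and defines no analysis set. The same section uses the word subjects for everyone who has the MRI and the PET scan, so the opening sentence can be read as the list of assessments each of the 150 participants receives. Group targets of 50 are most naturally worked as quotas, with recruitment into a group continuing until it is full.

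**5. What depends on the tracer name.** Nothing numerical. No variance, effect size or sample size was taken from 18F-THK-5351 data. The Investigational Agent section, the Study Design section, the primary outcome and the sentence directly after the slip all name 18F-MK-6240.

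**The case for a change.** The strongest case for acting is that both facts are verifiable and would cost only wording to tidy. The same number stands before and after a step that can exclude people, with no allowance or replacement rule. The tracer named in the sample-size paragraph is wrong on any reading. Where there is no power calculation, the group count is all a reader has, so the plan ought to say whether 150 means screened or scanned.

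The facts stand, and someone editing the document for another reason could clarify both. The consequence does not follow. The missing replacement rule is a gap that a study team fills as a matter of course when it recruits to group targets. A null result would be judged from the achieved numbers and the confidence interval, so the planned count cannot mislead at that stage. The number available for the CSF analyses depends in any case on the lumbar puncture, which participants may decline while staying in the study.

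Adding a detectable difference would bring little. With no standard deviation in the documents it could be given only in SD units, as above, and the stated aim is to gather information on a tracer rather than to test a prespecified effect.

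**Conclusion.** No change to the plan is needed. The screening count is ambiguous, and the target is missed only if people are excluded and not replaced, which the plan does not say. The tracer name is a clerical slip, apparently text carried over from work with the other tracer, and no figure depends on it.

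If the literal reading were right, a 5% to 10% loss would lower power from 80% to between 77.8% and 75.3% and raise the detectable f from 0.256 to between 0.263 and 0.270. These figures rest on an assumed exclusion rate, an assumed two-sided 5% level and an effect chosen to give 80% power at 150; the documents supply none of the three. A 20% loss would matter more, with power at 69.8%, but nothing in the text points to it. In every case the one-way ANOVA remains a valid test of the three groups and its conclusions would be drawn from the subjects actually scanned.

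### The primary one-way ANOVA pools one variance over normal, MCI and AD subjects; if SUVR spread differs by stage, the test can lose power and pooled stage contrasts are miscalibrated.

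*Combined protocol and SAP*

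**What the plan says.** The outcome is stated under Statistical Methods: "The primary outcome measure will be regional standardized uptake value ratio (SUVR) values". The analysis follows: "Analysis will be performed using a one-way ANOVA with cognitive status (AD vs. MCI vs. normal) as independent variable". The same section adds one further step for this outcome: "Effect of age and education will be determined in post-hoc analysis". No Welch or robust version, transformation, variance check, alpha level or procedure for comparing pairs of stages is named.

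Under Study Design, the target is given as "50 amnestic MCI and 50 Alzheimer's disease) and 50 elders without impairment (150 subjects total", that is, 50 + 50 + 50 = 150. The same section says "150 subjects will undergo screening including history, physical examination, routine laboratory studies, neuropsychological testing, and brain MRI".

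No SUVR standard deviation is given for any group. The Sample Size Determination section says "we do not have adequate preliminary data for a formal power calculation". The primary objective is to "determine the extent and spatial distribution of tau at different stages along the cognitive spectrum of aging".

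**The concern.** SUVR is target uptake divided by cerebellar uptake. Where there is little tau, the ratio has little to vary over. Where tau is present, it varies with the amount. The three groups are chosen to span that range, so equal spread cannot be taken for granted, and the plan offers no data that would support it.

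The objective concerns tau at different stages. An overall F test cannot say which stages differ, so contrasts between stages are the natural next step. If those contrasts use the ANOVA's pooled error, a wide-spread group lengthens the intervals of comparisons it does not take part in and shortens those of comparisons it does. At stake are the sensitivity of the normal-vs-MCI comparison, where early tau would show, and the false-positive rate of MCI vs AD. The F test itself may also lose sensitivity.

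**Working it through.** **Inputs from the documents.** One-way ANOVA on SUVR, three groups, target 50 per group. The plan states no alpha, SD, effect size or power, so there is no figure of its own to reproduce.

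**Assumed inputs.** Two-sided alpha 0.05; unadjusted contrasts; normally distributed data; SD ratios normal:MCI:AD from 1:1:1 to 1:3:5, plus 1:3:2, in which MCI varies most. For power, the normal-vs-MCI difference was set so that an unequal-variance (Welch) contrast has about 80%.

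**Step 1: size of the SE error.** With equal n, the pooled and true variances of a contrast between groups a and b compare as

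(pooled SE / true SE)² = [2(s₁² + s₂² + s₃²)/3] / (s_a² + s_b²).

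At 1:2:3 the numerator is 2 × 14/3 = 9.33, so:
- normal vs MCI: √(9.33/5) = 1.37, interval too wide
- MCI vs AD: √(9.33/13) = 0.85, interval too narrow
- normal vs AD: √(9.33/10) = 0.97

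**Step 2: when normal vs MCI suffers.** The ratio exceeds 1 when 2(s₁² + s₂² + s₃²)/3 > s₁² + s₂², which reduces to s₃² > (s₁² + s₂²)/2. The AD variance must exceed the mean of the other two. At 1:3:2 it does not (4 < 5), and the ratio is √(9.33/10) = 0.97.

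**Step 3: error rates and power.** At 1:2:3 the pooled normal-vs-MCI test in effect uses a critical value of 1.96 × 1.366 = 2.68, which gives about 0.7% error. For MCI vs AD it is 1.96 × 0.847 = 1.66, about 9.7%. Simulation at 50/50/50 (40,000 data sets per scenario) agrees:

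| SD ratio | F test error | Pooled error, normal–MCI | Pooled error, MCI–AD | Pooled error, normal–AD | Normal–MCI power, pooled vs Welch |
|---|---|---|---|---|---|
| 1:1.5:2 | 5.5% | 1.7% | 8.5% | 5.5% | 66% vs 79% |
| 1:2:2 | 5.7% | 3.2% | 9.0% | 3.2% | 74% vs 79% |
| 1:2:3 | 6.0% | 0.8% | 9.7% | 5.7% | 55% vs 80% |
| 1:2:4 | 6.8% | 0.1% | 10.3% | 7.5% | 32% vs 79% |
| 1:3:3 | 5.8% | 2.9% | 10.0% | 2.8% | 72% vs 79% |
| 1:3:5 | 6.5% | 0.4% | 10.5% | 6.4% | 41% vs 78% |
| 1:3:2 | 6.1% | 5.9% | 9.6% | 0.8% | 82% vs 79% |

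Repeat runs move the error rates by a few tenths of a point and power by about a point. Welch's F and the Welch contrasts stayed at about 5% in every row. With equal SDs, normal-vs-MCI power is 80.3% pooled and 80.0% Welch.

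**Step 4: power of the F test itself.** MCI and AD were shifted from normal by the same amount (an assumed early-rise pattern). Power of the classical against Welch's F was 71% vs 84% at 1:1.5:2, 59% vs 83% at 1:2:3, and 48% vs 83% at 1:3:5. The gap applies to this pattern of means; it does not show that Welch's F is superior for every pattern.

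**Step 5: unequal attained sizes (normal/MCI/AD).** At 50/45/30 the classical F has 10.0% error (1:2:3) and about 11.5% (1:3:5). At 30/45/50 it is about 3.7% to 3.9% for the same SDs. At 50/48/47 it is 6.3% to 6.9%.

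**Step 6: skew.** With exponential data in MCI and AD at 50/50/50, Welch's F has 6.5% error (1:2:3) and 7.3% (1:3:5), the same as the classical F. At 50/45/30 Welch's F has 7.5% to 8.2%.

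**The case against.** The strongest reply is that the plan names an overall F test and no pairwise contrast. Its only post-hoc step concerns age and education, and the F test is close to nominal at equal n. This stands for type I error. It does not cover power, where the named test can itself fall well short (Step 4). Nor does it remove the need for stage contrasts, since the objective is about stages.

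A second reply is that unequal variance is nowhere shown. That is right, and every consequence here is conditional on it. A reader might infer that the planned analysis has wrong error bars as it stands; with no group SDs in the documents, that cannot be said.

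Third, the loss for normal vs MCI depends on which group varies most. It is modest at 1:2:2 and 1:3:3 and absent at 1:3:2. This stands too, although in the last case MCI vs AD and normal vs AD are miscalibrated instead.

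Fourth, the 9.7% assumes unadjusted, ungated contrasts. Under the same null, Tukey's procedure brings MCI vs AD to 4.7%, and testing pairs only after a significant F brings it to 5.3%. Neither cures the conservatism of normal vs MCI.

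Fifth, a reader might infer from screening 150 for a target of 150 that imbalance will inflate the F test. Read literally, any exclusion leaves fewer than 150, and nothing keeps the groups equal. But the documents do not suggest heavy losses confined to AD; the MRI exclusions they mention are for pathology unrelated to it. Modest losses change little, and if the normal group ends up smallest the test becomes conservative.

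Finally, a reader might infer that pooling would overstate late-stage differences. It does not: group means and their differences are unaffected, and only standard errors, intervals and p-values change.

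**Conclusion.** The point holds in conditional form. The plan relies on an equal-variance method for an outcome whose spread may well differ by stage, and gives no data or safeguard on the matter.

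If spread differs, the F test at 50/50/50 has roughly correct type I error but can lose power: 13 to 35 points over the assumed early-rise scenarios (84 − 71 = 13; 83 − 48 = 35). In every unequal-variance scenario tried, at least one pooled stage contrast was miscalibrated. Unadjusted MCI vs AD ran at 8.5% to 10.5%. Normal vs MCI ran as low as 0.1% and lost up to 47 points of power (79 − 32), but only when the AD variance exceeded the mean of the other two. Unequal attained sizes push the F test either way, depending on which group is smallest.

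This is an inexpensive improvement in robustness. It does not show that the planned test is invalid. The sizes rest wholly on assumed SD ratios, alpha, effect sizes and attained group sizes, and, apart from the skewed-data check, on normal data.

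**What to change.** Replace the ANOVA sentence in Statistical Methods with:

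> For each region, groups will be compared by Welch's one-way ANOVA, followed by normal-vs-MCI, MCI-vs-AD and normal-vs-AD contrasts with unequal-variance (Games-Howell) standard errors and 95% CIs; where covariates are included, HC3 standard errors will be used.

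Add an analysis of log SUVR as a sensitivity analysis, because Welch's F does not by itself deal with skew: its error stays at about 6% to 8% in the skewed scenarios. The HC3 clause covers the age and education analysis already planned.

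The cost is one replaced sentence and one added sensitivity analysis, with no new data. If the variances turn out equal, the loss for normal vs MCI is 80.3% − 80.0% = 0.3 points of power.

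### The secondary regressions of tau binding name no age covariate (and no education covariate for cognition), so an age-driven association can be reported as a relation between tau and a marker

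*Combined protocol and SAP*

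**What the plan says.** Statistical Methods describes two analyses of SUVR. The first compares groups: "Analysis will be performed using a one-way ANOVA with cognitive status (AD vs. MCI vs. normal) as independent variable". The next sentence is the only mention of age and education in the Statistical Plan: "Effect of age and education will be determined in post-hoc analysis". A new paragraph then sets out the secondary regressions, with tracer "binding as dependent variable and cognitive scores, voxel count on MRI, and CSF concentrations of markers of inflammation and neurodegeneration as independent variables". No further covariate is named for them.

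These regressions serve the secondary objectives, which ask how "binding in brain relates to cognitive performance, amyloid binding, atrophy on MRI, and CSF concentrations of markers of inflammation and neurodegeneration", and the single secondary outcome, "Correlation Between Tau, Neurodegeneration and Inflammation". Study Design sets a target of 150 subjects, 50 in each group. Lumbar puncture is optional ("Subjects may refuse the LP and still participate in the other study procedures"), so the CSF models may have fewer than 150 observations. The expected uptake is not given.

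**The concern.** The plan regards age and education as worth examining for SUVR but does not carry them into the models that relate SUVR to cognition, atrophy and CSF. In those models age may be related to both sides. The unadjusted slope then includes the product of the two age relations, even when tau and the marker are unrelated among people of the same age. Adjusting the ANOVA would not change these slopes, because they are separate models.

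Education raises a narrower question, for cognition only. It may shift test scores, and may or may not be related to tau.

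No other analysis is described for the objectives on cognition, atrophy and CSF, or for the secondary outcome. Followed as written, the plan could report a correlation of tau with atrophy or inflammation that comes from age.

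**Working it through.** **Inputs from the documents.** Maximum n is 150 (Study Design). The CSF sample is unknown; n=75 assumes that half the subjects accept lumbar puncture. The plan states no alpha, effect size, SD or correlation, so it has no figure to reproduce.

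**Assumed inputs.** Two-sided 0.05; one marker per model; age correlations of 0.2-0.3 with SUVR and 0.35-0.5 with the marker, plus a low case of 0.1 and 0.2.

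**Step 1: age-driven correlation.** If SUVR and the marker are unrelated at a given age, their unadjusted correlation is

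ρ = r(age, SUVR) × r(age, marker).

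This gives 0.2 × 0.35 = 0.07, 0.2 × 0.5 = 0.10, 0.3 × 0.5 = 0.15, and in the low case 0.1 × 0.2 = 0.02.

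**Step 2: chance of p<0.05.** In a one-predictor regression the slope test is the test of the correlation. By Fisher's z, d = atanh(ρ) × √(n − 3), and the rejection rate is Φ(d − 1.96) + Φ(−d − 1.96). For ρ=0.15 and n=150, d = 0.1511 × 12.124 = 1.832, which gives 44.9%.

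| Age correlations (SUVR, marker) | ρ | n=150, Fisher z | n=150, simulated | n=75, Fisher z | n=75, simulated |
|---|---|---|---|---|---|
| 0.1, 0.2 | 0.02 | 5.7% | 6.4% | 5.3% | – |
| 0.2, 0.35 | 0.07 | 13.6% | 12.7% | 9.1% | 9.4% |
| 0.2, 0.5 | 0.10 | 22.9% | 23.7% | 13.6% | 13.7% |
| 0.3, 0.5 | 0.15 | 44.9% | 45.4% | 25.0% | 24.9% |

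The simulation used 4,000 replicates. With age in the model it rejected 4.7-5.2% of the time, but there age was the only shared cause.

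**Step 3: what age adjustment leaves.** In a second simulation (n=150, 50 per group), SUVR rose 1 SD per stage, the marker differed by 0.3-0.5 SD between AD and normal, and there was no relation within a stage. These values are also assumed. The age-adjusted slope still rejected about 17-39% of the time. Adding diagnosis brought this to about 5%.

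**Step 4: education and the slope on cognition.** Write r_tc for the correlation of tau with cognition, r_ce for cognition with education, and r_te for tau with education. In standardised form the unadjusted slope is r_tc and the adjusted slope is (r_tc − r_te × r_ce)/(1 − r_ce²).

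- If r_te = 0, the ratio of unadjusted to adjusted slope is 1 − r_ce². For r_ce = 0.3, 0.4 and 0.5 it is 0.91, 0.84 and 0.75, an understatement of 9-25%.
- The two slopes are equal when r_te = r_tc × r_ce. With r_tc = −0.5 and r_ce = 0.3 or 0.4, that is −0.15 or −0.20. With r_tc = −0.3 it is −0.09 or −0.12. A more negative r_te produces overstatement.
- Example: r_tc = −0.3, r_ce = 0.4 and r_te = −0.2 give an adjusted slope of (−0.3 + 0.08)/0.84 = −0.262, against −0.30 unadjusted, which is too steep by about 15%.

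**The case against.** - **The post-hoc sentence may cover the regressions.** It concerns the same dependent variable and is not expressly confined to the ANOVA. That is possible, but the sentence precedes the regression paragraph and does not make either variable a covariate in any model. On the wide reading, adjustment would still be post hoc and unspecified.
- **The stakes are modest.** The protocol says it aims to generate information, and it sets no alpha. The p<0.05 rates are therefore an imported yardstick and the correlations are assumed; in the low case almost nothing is lost. This stands, and it limits the point to a cheap improvement in the secondary analyses.
- **The models may be joint.** The independent variables are listed together and could enter one model. The rates above apply to one-marker models only.
- **A reader might infer that the relation of tau to cognition will be understated.** The documents do not support this. It needs education to be unrelated to SUVR and scores to be raw. The plan itself leaves an education effect on SUVR open and does not say whether scores are normed. Step 4 shows that the bias can go either way.
- **A reader might infer that adding age restores a 5% error rate.** That holds only if age is the sole shared cause. In a sample recruited from three cognitive stages this cannot be assumed, as Step 3 shows. Whether to condition on stage is a separate and debatable choice.
- **A reader might extend the list to sex.** The documents do not mention sex and give no basis for adding it on this point.

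**Conclusion.** The concern holds in a limited form. The regression sentence omits age and education, and nothing elsewhere in the document brings them in. Any age relation shared by SUVR and a marker therefore stays in the slope. For one-marker models with the assumed moderate correlations, the chance of p<0.05 with no relation at a given age is about 13-45% at n=150 and 9-25% at n=75. With correlations of 0.1 and 0.2 it is about 6%. These are illustrations under assumed inputs and do not estimate this study's error rate. They do not show that any particular association will be spurious.

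For education, the conclusion is only that the slope on cognition can be biased if scores are not education-normed, in a direction that depends on how education relates to SUVR. The primary group comparison is outside this point.

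**What to change.** Add to the regression paragraph of Statistical Methods:

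> Each secondary regression will include age as a covariate, and the cognitive-score regressions will also include education unless scores are already education-normed; the slope without these covariates will be reported beside it.

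Base the secondary conclusions on the adjusted slope. State in the report that adjustment removes the age-driven part (and, for cognition, the education-driven part) and does not remove differences shared across the AD, MCI and normal groups.

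The cost is one sentence and one or two degrees of freedom per model. Both variables are already named in the plan, so no new procedure is needed. The adjusted slope answers a narrower question, namely the relation at a given age and, for cognition, a given education. Reporting the unadjusted slope beside it keeps the broader description available.

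### The tau–atrophy analysis names voxel count as its MRI predictor and states no head-size adjustment, so head size is mixed with tissue loss

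*Combined protocol and SAP*

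**What the plan says.** All references are to the combined protocol and SAP.

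- **Study Objectives** (secondary objectives) asks how binding relates to "cognitive performance, amyloid binding, atrophy on MRI, and CSF concentrations" of inflammatory and neurodegenerative markers.
- **Study Design** provides a single structural scan: "One brain MRI will be performed on each subject using a 3 T Philips scanner". The T1 sequence is "3D T1 (MPRAGE, 180 slice 1 mm resolution, 256 x 256 voxel count) for volumetric analysis". FreeSurfer is to derive eleven ROIs from it.
- **Statistical Methods**, final paragraph: "Regression models will be fit for ¹⁸F-MK-6240 binding as dependent variable and cognitive scores", followed by "voxel count on MRI, and CSF concentrations of markers of inflammation and neurodegeneration as independent variables". The paragraph does not say which region is counted or whether the count is scaled to anything.
- **Covariates.** The only ones named are in the preceding ANOVA paragraph: "Effect of age and education will be determined in post-hoc analysis". Sex, head size and intracranial volume are not mentioned in any section.

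**The concern.** Atrophy means loss of tissue. With cross-sectional data it has to be inferred from size, and absolute size is the size the structure started from minus what has been lost. A subject with a small head and no atrophy can have the same count as a subject with a large head and considerable atrophy.

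The voxel count is on the predictor side of the regression. Variation in the predictor that is not atrophy therefore does more than widen the confidence interval: it changes the slope being estimated. More subjects or perfect segmentation would not remove this, and it would also arise within one diagnostic group. At stake is whether the reported association answers the secondary objective on atrophy or a mixture of atrophy and head size.

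**Working it through.** **Plan's own figure.** There is none to reproduce. The plan gives no slope, correlation, variance or power, and Sample Size Determination says that a formal power calculation was not possible. The target of 50 + 50 + 50 = 150 subjects is consistent. What follows explores size under stated assumptions.

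**Inputs from the document.** Binding is the dependent variable, voxel count is a predictor, the T1 resolution is 1 mm (so a count is in effect an absolute volume), there is one MRI per subject, and n = 150.

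**Assumptions.** The correlation of head size with regional volume is 0.4 to 0.6, so s = 0.4² to 0.6² = 0.16 to 0.36. The correlation of tau with preserved volume is −0.40 (less preserved tissue, more tau). Tests use two-sided alpha 0.05. Each model has one MRI predictor.

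**Step 1: head size unrelated to tau.** Write volume V = P + H, where P is the part reflecting preserved tissue, H is head size, the two are uncorrelated, and s = var(H)/var(V). The slope wanted is b = cov(tau, P)/var(P). The slope obtained is cov(tau, P)/var(V) = b(1 − s). The correlation obtained is r√(1 − s).

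| s | slope factor | correlation factor | r = −0.40 appears as |
|---|---|---|---|
| 0.10 | 0.90 | 0.95 | −0.38 |
| 0.16 | 0.84 | 0.92 | −0.37 |
| 0.25 | 0.75 | 0.87 | −0.35 |
| 0.36 | 0.64 | 0.80 | −0.32 |

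**Step 2: effect on the test.** By Fisher z, power ≈ Φ(√(n − 3) · atanh|r| − 1.96).

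- |r| = 0.40, n = 150: √147 × 0.4236 − 1.96 = 3.18, power above 99%.
- |r| = 0.32, n = 150: √147 × 0.3316 − 1.96 = 2.06, power about 98%.
- The same two values in one group of 50: about 83% and 62%.
- True |r| = 0.25, n = 150: 87% with s = 0, 79% with s = 0.2, 66% with s = 0.4.

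**Step 3: head size related to tau.** Let ρ = corr(tau, P) and c = corr(tau, H). The ratio of the slope obtained to the slope wanted is (1 − s) + (c/ρ)√(s(1 − s)). With assumed ρ = −0.3 and s = 0.3, √(0.3 × 0.7) = 0.458, and:

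| c | −0.3 | −0.2 | −0.1 | 0 | +0.1 | +0.2 | +0.3 |
|---|---|---|---|---|---|---|---|
| slope ratio | 1.16 | 1.01 | 0.85 | 0.70 | 0.55 | 0.39 | 0.24 |

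The slope may therefore be too small, about right, or too large.

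**Step 4: does adjustment work?** If tau = bP + gH + error, substituting P = V − H gives tau = bV + (g − b)H + error. With H in the model, the coefficient of V is b whatever g is, provided that intracranial volume measures H well. A simulation of the multiplicative case (volume = intracranial volume × preserved fraction, head size unrelated to tau) assumed coefficients of variation of 8–12% for head size and 10–20% for preserved fraction. The unadjusted slope was 0.41 to 0.86 of the true value. With intracranial volume as a covariate it was 0.99 of the true value.

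**The case against.** The strongest reply is that the plan is brief rather than wrong. It never says that the count is unadjusted, and Study Design uses the same term for the image matrix, so the wording may be loose. The T1 is intended for volumetric work, and an analyst could normalise without departing from the text. This stands in part: absence of adjustment is read from silence. But voxel count is what the plan names, and nothing in it leads to a head-size-adjusted measure. Followed as written, it yields an absolute size.

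Three stronger readings are tempting, and the documents do not support them.

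- **A reader might infer that the slope must shrink toward zero.** That holds only if head size is unrelated to tau. Step 3 shows exaggeration is also possible, and the documents have no data on the point.
- **A reader might infer that having one MRI is the fault.** The objectives are cross-sectional and no section claims to measure change. A single head-size-adjusted volume is a legitimate proxy. The single scan only makes a head-size reference necessary.
- **A reader might infer a serious loss of power.** At a correlation of 0.40 and n = 150 the loss is about one or two percentage points. It becomes material only for a weaker correlation or for one group of 50.

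Two further reservations stand. In the pooled sample, disease adds variance to volume, so s may be below the assumed range. And if cognitive scores, voxel count and CSF markers enter one model together, the simple factor (1 − s) no longer applies as it is.

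**Conclusion.** The point holds as a gap between a stated secondary objective and the variable named to serve it. The MRI predictor is an absolute size with no region named and no head-size adjustment stated, so the analysis does not isolate atrophy.

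Under the assumptions that head size explains 16–36% of volume variance and is unrelated to tau, the slope is 16–36% too small. The correlation, which is closer to how the secondary outcome is worded, is 8–20% too small. If head size is related to tau, for instance because sex is related to both and is not in the model, direction and size are open. An unadjusted estimate could not then be presented as conservative.

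Confidence is high in the omission and low in any particular magnitude, because every variance share and correlation used here is assumed. The primary comparison of SUVR across cognitive groups does not use voxel count and is untouched. The change should be made, but the main result of the study does not depend on it.

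**What to change.** In the regression paragraph of Statistical Methods:

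1. Replace voxel count with the regional volume of FreeSurfer ROIs, and name which of the eleven are used.
2. Pre-specify estimated intracranial volume, taken from the FreeSurfer run on the same T1, and sex as covariates in every model relating tau to volume.
3. Describe the result as an association with cross-sectional, head-size-adjusted volume.

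The cost is a few lines of SAP text and one or two extra model terms. No additional scan, visit or subject is needed. Fixing the choice in advance also removes the option of reporting whichever of the adjusted and unadjusted results looks better.
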